1.4 Dose Rationale

1.4.1 Rationale for Starting Dose

The optimal dose and regimen of IMC-CS4 in humans are not known. The proposed starting dose and regimen of IMC-CS4 was 2.5 mg/kg administered qw by I.V. infusion. This starting dose was based on the following rationale:

- IMC-CS4 was well tolerated in cynomolgus monkeys when administered qw at 20, 60, or 180 mg/kg by I.V. infusion for 4 weeks. The key toxicological findings included periorbital swelling, increased serum transaminases, and immunomodulatory effects on monocytes, neutrophils, spleen, Kupffer cells, and bone marrow. As none of the observed effects were considered adverse, the NOAEL was identified as 180 mg/kg.
- Most antibodies and other large proteins scale best between species when doses are compared directly in mg/kg (FDA 2005). Given the similar binding affinities of IMC-CS4 to human and monkey CSF-1R, this approach predicts that 20 mg/kg in humans will have similar findings as in the monkey at the same dose, and that a dose equal to one-eighth of this (2.5 mg/kg), would be an acceptable and safe starting dose for this first-in-human study in oncologic indications. This starting dose is 72-fold lower than the NOAEL (180 mg/kg).
- A noncompartmental PK analysis of IMC-CS4 in cynomolgus monkeys of serum sampled following the fourth infusion, where the drug is at or approaching steady state, indicated a mean (sex-combined) elimination half-life of 158, 243, and 470 hours (approximately 7 to 20 days) for the 20, 60, and 180 mg/kg doses, respectively, and is supportive of a dosing interval of equal to or greater than qw.
- The target serum trough concentration for IMC-CS4 based on antitumor activity of the surrogate antibody CS7 in a murine model of breast cancer is approximately 425 $\mu\text{g}/\text{mL}$.

To further support identification of the appropriate IMC-CS4 dose and regimen to attain these serum concentrations, simulations based on the mathematical modeling of serum concentration data of IMC-CS4 derived from the cynomolgus monkey PK study were used. A one-compartment model best fit the data. The simulations were based on the following assumptions:

1. The one-compartmental model was applicable to the simulated doses.
2. PK parameters obtained from the 20-mg/kg dose monkey PK study and elimination half-life values were applicable to human PK dosing and regimens.
3. IMC-CS4 drug levels following the fourth infusion were at or near steady state.

The concomitant elevation in CSF-1 serum levels and the increase in the serum levels of CK, LDH, and AST suggest pharmacodynamic activity of IMC-CS4. Since preclinical studies with IMC-CS4 in monkeys demonstrated a dose-response correlation between the dose of IMC-CS4 and the increase in serum enzyme levels, a dose escalation was considered likely to result in a DLT. Therefore, it was considered medically prudent not to dose escalate further as initially planned.

In order to better characterize the IMC-CS4 dose-response effect on the monocyte / macrophage system and on various serologic and hematologic parameters, the dosing scheme and schedule was amended in Protocol Amendment Version 3.0 to reflect dose reductions and prolonged administration intervals as follows: Under Version 2.0 of the protocol, dose escalation was to begin at 2.5 mg/kg in Cohort 1 and proceed to 5, 10, 20, and 30 mg/kg (all qw) in Cohorts 2 to 5, respectively. Following completion of Cohort 1 (2.5 mg/kg), the dose-escalation scheme was revised to 0.3 mg/kg qw in Cohort 2, 0.6 mg/kg qw in Cohort 3, 1.25 mg/kg every 2 weeks (q2w) in Cohort 4, 1.25 mg/kg qw in Cohort 5, and 2.5 mg/kg q2w in Cohort 6 (a newly added cohort). The addition of q2w dosing was deemed reasonable based on the relatively long half-life observed in cynomolgus monkeys.

Further rationale for the revised dose-escalation scheme was as follows. The second cohort started at approximately an 8-fold lower dose level (0.3 mg/kg administered qw) than the study starting dose (2.5 mg/kg qw in Cohort 1). Additionally, certain doses (1.25 and 2.5 mg/kg) were to be administered on both qw and q2w regimens to facilitate PK/PD characterization. Upon completion of all 6 planned cohorts, the PK/PD and safety profiles were to be evaluated to assess if further dose escalation and/or regimens were warranted to determine the recommended Phase 2 dose (RP2D).

1.4.3 Clinical Experience from Cohorts 2 through 5

This section describes the clinical experience after the revised dose-escalation scheme was implemented in Protocol Amendment Version 3.0, specifically, the clinical observations for Cohorts 2, 3, 4, and 5. No DLTs were observed in Cohorts 2 and 3. The clinical data generated for subjects treated in Cohorts 2 and 3 indicate that IMC-CS4 is safe and well tolerated when administered as 4 qw doses (0.3 or 0.6 mg/kg) followed by 2 weeks of recovery.

[figure not shown]

1.4.4 Exploring Non-Weight-Based Dosing (Cohorts 6a through 8c)

[figure not shown]
Exploratory graphical analysis of the pharmacokinetics of IMC-CS4 in Cohorts 1 to 5 indicates no clear relationship between body weight and drug clearance ([Figure 1](#)). Furthermore, weekly dosing results in sustained elevation of CSF-1, an indicator of target engagement, for the duration of the dosing period ([Figure 2](#)). In contrast, dosing every 2 weeks allows CSF-1 levels to return to baseline, indicating reduced target engagement with a more intermittent dosing schedule. Therefore, additional cohorts are being added in this protocol amendment, Version 7.0, to evaluate safety, pharmacokinetics, and pharmacodynamics of non-weight-based dosing of IMC-CS4 administered on a weekly schedule. As was done for weight-based dosing cohorts, doses for non-weight-based dosing cohorts will be escalated to identify RP2D. To accommodate these new non-weight-based dosing cohorts, the definition of DLT has been

revised and an algorithm added to initiate steroid therapy early during the course of an immune-related adverse event (irAE) (refer to Section 9.1.1 for additional details).

Abbreviations: QW = weekly; Q2W = every 2 weeks.

Figure 1. **Reported body weight versus LY3022855 drug clearance (as determined using non-compartmental analysis) for eligible subject data from Study JSCA (IMCL CP24-1001.)**

Profile plot of CD14DIM CD16BR MONO (CELLS/uL)
Program Location: F:/lillyce/prd/ly3022855/i5f_ie_jsca/misc1/programs_nonsdd/CS4_jsca_CD14dimCD16br_C4-C5.r
Data Location: F:/lillyce/prd/ly3022855/i5f_ie_jsca/misc1/data/shared/custom/dm.csv
Data Location: F:/lillyce/prd/ly3022855/i5f_ie_jsca/misc1/data/shared/custom/lb.csv
Output Location: F:/lillyce/prd/ly3022855/i5f_ie_jsca/misc1/programs_nonsdd/tfl_output/CS4_JSCA_CD14dimCD16br_C4-C5.rtf

Figure 2. Profile review of CD14^{DIM} CD16^{BR} MONO (cells/µL).

1.5 Human Experience

This is the first study of IMC-CS4 in humans. Limited data are available from this study to date, and are described in Sections 1.4.2 and 1.4.3.

More information about the known and expected benefits, risks, and reasonably anticipated adverse events (AEs) may be found in the IB. Information on AEs expected to be related to the investigational product may be found in Section 7 (Development Core Safety Information) of the IB. Information on serious adverse events (SAEs) expected in the study population independent of drug exposure and that will be assessed by the Sponsor in aggregate, periodically during the course of the study, may be found in Section 6 (Effects in Humans) of the IB.

NOTE:

Protocol Amendment Version 7.0 describes additional cohorts for non-weight-based dosing of IMC-CS4, which will be referred to as Part B of the study. Cohorts described in the protocol prior to Protocol Amendment Version 7.0 (that is, for weight-based dosing of IMC-CS4) will now be referred to as Part A of the study. Refer to Section [4.1](#) for details of the dose assignments for Parts A and B.

Throughout the protocol, information relevant only to Part A (weight-based dosing) or only to Part B (non-weight-based dosing) is indicated as such. Any information not indicated as “Part A only” or “Part B only” is relevant to both parts.

2 STUDY OBJECTIVES

2.1 Primary Objectives

The primary objectives of this study are to establish the safety profile and characterize the pharmacokinetic (PK) profile of IMC-CS4 in the treatment of subjects with advanced solid tumors refractory to standard therapy or for which no standard therapy is available.

2.2 Secondary Objectives

The secondary objectives of this study are:

- Part A only – To define the recommended Phase 2 dose (RP2D) using weight-based dosing;
- Part B only – To define the RP2D using non-weight-based dosing;
- To characterize the pharmacodynamic profile of IMC-CS4 on circulating levels of CSF-1; and
- To assess the development of antibodies against IMC-CS4 (immunogenicity).

2.3 Exploratory Objectives

The exploratory objectives of this study are:

- To assess pharmacodynamic response markers including, but not limited to, interleukin-34 (IL-34) and MCP-1;
 - To assess the impact of IMC-CS4 monotherapy on LDH, CK, and AP isoenzymes;
 - To assess the pharmacodynamic impact of IMC-CS4 on selected cellular and molecular markers to establish a potential correlation with safety and antitumor activity;
 - To assess the pharmacodynamic impact of IMC-CS4 on various components of the monocyte-macrophage system in hematologic or tissue specimens;
 - To assess the impact of IMC-CS4 monotherapy on bone metabolism; and
 - To assess the antitumor activity of IMC-CS4 as monotherapy in the treatment of advanced solid tumors.

3 STUDY POPULATION SELECTION

3.1 Study Population

Subjects will be recruited from a population of cancer subjects treated at the investigational centers. A record of the most recent pretreatment evaluations will be reviewed to determine the eligibility of a subject for this study.

3.2 Inclusion Criteria

Each subject must meet the following criteria to be enrolled in this study:

1. The subject has a histologic or cytologic confirmation of advanced solid tumors that are refractory to standard therapy or for which no standard therapy is available.
2. The subject has measurable or nonmeasurable disease according to the Response Evaluation Criteria in Solid Tumors, Version 1.1 (RECIST 1.1; see Section 11).
3. The subject has resolution to Grade ≤ 1 by the National Cancer Institute Common Terminology Criteria for Adverse Events (NCI-CTCAE), Version 4.03, of all clinically significant toxic effects of prior chemotherapy, surgery, radiotherapy, or hormonal therapy (with the exception of alopecia).
4. The subject has an Eastern Cooperative Oncology Group performance status (ECOG PS) score of 0-2.
5. The subject has adequate hematologic function, as defined by:
 - Absolute neutrophil count (ANC) $\geq 1500/\mu\text{L}$;
 - Hemoglobin $\geq 9 \text{ g/dL}$ (5.58 mmol/L); and
 - Platelets $\geq 100,000/\mu\text{L}$.
6. The subject has adequate hepatic function, as defined by:
 - Bilirubin ≤ 1.5 times the upper limit of normal (\times ULN); and
 - AST and ALT $\leq 2.5 \times$ ULN ($\leq 5 \times$ ULN in the presence of known liver metastases).
7. The subject has adequate renal function as defined by creatinine clearance $\geq 50 \text{ mL/min}$ measured either by 24-hour urine collection or calculated using the Cockcroft-Gault formula.
8. The subject must have adequate coagulation function as defined by:
 - International Normalized Ratio (INR) ≤ 1.5 ; and
 - Prothrombin time (PT) and partial thromboplastin time (PTT) or activated PTT $\leq 1.5 \times$ ULN.
9. The subject has CK \leq ULN.
10. The subject has a life expectancy >3 months.
11. The subject is 18 years of age or older.
12. The subject (women of childbearing potential [WOCBP] or fertile men with partners of childbearing potential) agrees to use adequate contraception during the study period and for 12 weeks after the last dose of study therapy.
13. The subject has provided signed informed consent.

14. The subject is accessible for treatment and follow-up; subjects enrolled in this trial must be treated at the study center.
15. The subject must undergo mandatory biopsies, including one pretreatment and one posttreatment tumor biopsy procedure (refer to tumor biopsy Section [7.2.1.1](#)).

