Throughout this protocol, “days” refers to calendar days, unless otherwise indicated.

Study Population:

It is anticipated that approximately 72 subjects will be enrolled in approximately 6 study sites in the United States.

Inclusion/Exclusion Criteria:

Inclusion Criteria

Each subject must meet the following criteria to be enrolled in this study:

1. The subject has a histologic or cytologic confirmation of advanced solid tumors that are refractory to standard therapy or for which no standard therapy is available.
2. The subject has measurable or nonmeasurable disease according to the Response Evaluation Criteria in Solid Tumors, Version 1.1 (RECIST 1.1).
3. The subject has resolution to Grade ≤ 1 by the National Cancer Institute Common Terminology Criteria for Adverse Events (NCI-CTCAE), Version 4.03, of all clinically significant toxic effects of prior chemotherapy, surgery, radiotherapy, or hormonal therapy (with the exception of alopecia).
4. The subject has an Eastern Cooperative Oncology Group performance status (ECOG PS) score of 0-2.
5. The subject has adequate hematologic function, as defined by:
 - Absolute neutrophil count (ANC) $\geq 1500/\mu\text{L}$;
 - Hemoglobin $\geq 9\text{ g/dL}$ (5.58 mmol/L); and
 - Platelets $\geq 100,000/\mu\text{L}$.
6. The subject has adequate hepatic function, as defined by:
 - Bilirubin ≤ 1.5 times the upper limit of normal (\times ULN); and
 - AST and ALT $\leq 2.5 \times$ ULN (or $\leq 5 \times$ ULN in the presence of known liver metastases).
7. The subject has adequate renal function as defined by creatinine clearance $\geq 50\text{ mL/min}$ measured either by 24-hour urine collection or calculated using the Cockcroft-Gault formula.
8. The subject must have adequate coagulation function as defined by:
 - International Normalized Ratio (INR) ≤ 1.5 ; and
 - Prothrombin time (PT) and partial thromboplastin time (PTT) or activated PTT $\leq 1.5 \times$ ULN.
9. The subject has CK \leq ULN.
10. The subject has a life expectancy >3 months.
11. The subject is 18 years of age or older.
12. The subject (women of childbearing potential [WOCBP] or fertile men with partners of childbearing potential) agrees to use adequate contraception during the study period and for 12 weeks after the last dose of study therapy.
13. The subject has provided signed informed consent.

14. The subject is accessible for treatment and follow-up; subjects enrolled in this trial must be treated at the study center.

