3.3 Exclusion Criteria

Subjects who meet any of the following criteria will be excluded from the study:

1. The subject has experienced acute pathologic fracture or spinal cord compression within 28 days prior to first dose of study therapy.
2. The subject has a known hypersensitivity to monoclonal antibodies or to agents of similar biologic composition as IMC-CS4.
3. The subject has received treatment with any monoclonal antibodies within 4 weeks prior to first dose of study therapy.
4. The subject has undergone a major surgical procedure, open biopsy, radiofrequency ablation, or has experienced a significant traumatic injury within 28 days prior to enrollment.
5. The subject has a history of another primary cancer, with the exception of a) curatively resected non-melanomatous skin cancer; b) curatively treated cervical carcinoma in situ; or c) other primary solid tumor treated with curative intent, no known active disease present, and no treatment administered during the last 3 years prior to study entry.
6. The subject is receiving concurrent treatment with other anticancer therapy, including other chemotherapy, immunotherapy, chemoembolization, targeted therapy, or any investigational agent within 4 weeks prior to study entry, or radiotherapy within 2 weeks prior to study entry. An exception is that subjects with metastatic breast or prostate cancer who have been on a stable dose (≥ 28 days) of an approved hormonal agent will not be excluded (ie, they will be eligible). Subjects with breast cancer may also continue with concurrent human epidermal growth factor receptor 2 (HER2)-directed therapy.
7. The subject has known muscle damage due to a primary, traumatic, or other muscle disease.
8. The subject is known to be human immunodeficiency virus (HIV) seropositive.
9. The subject has a known and uncontrolled infection.
10. The subject is known to have active tuberculosis, leishmaniasis, or listeriosis.
11. The subject has a history of and/or current: symptomatic coronary artery disease, confirmed left ventricular ejection fraction (LVEF) $\leq 50\%$ or any cardiac insufficiency $>$ New York Heart Association (NYHA) class II,* uncontrolled hypertension, or serious cardiac arrhythmia (well-controlled atrial fibrillation is permitted).
12. Subjects with known history, or clinical or laboratory evidence of, liver disease. Notably, subjects with any of the following liver function abnormalities will be excluded:

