 - a Cirrhosis with evidence of portal hypertension or bridging fibrosis
 - b Alcoholic hepatitis
 - c Esophageal varices
 - d A history of bleeding esophageal varices
 - e Hepatic encephalopathy
 - f Ascites related to portal hypertension

- g Chronic viral hepatitis with total serum bilirubin >3 mg/dL.
- 13. The subject has active bleeding.
- 14. The subject has leukemia or lymphoma.
- 15. The subject has a known psychiatric illness/social situation (including alcohol and/or drug dependency) that, in the Investigator's opinion, would limit compliance with study requirements.
- 16. The subject has known or suspected primary brain or leptomeningeal tumors or metastases (subjects with a history of brain metastases must have received definitive surgery or radiotherapy, be clinically stable, and may not be taking steroids; subjects receiving anticonvulsants are eligible).
- 17. The subject is pregnant (confirmed by serum beta human chorionic gonadotropin [β -hCG] test performed within 7 days prior to first dose of study therapy) or breastfeeding.
- 18. The subject has received a solid organ transplant.
- 19. The subject has any other serious uncontrolled medical disorders that, in the opinion of the Investigator, would compromise the subject's safety or the ability of the subject to participate in the study.

*NYHA Congestive Heart Failure Classification (NYHA 1994):

Class I – Patients with no limitation of activities; they suffer no symptoms from ordinary activities.

Class II – Patients with slight, mild limitation of activity; they are comfortable with rest or with mild exertion.

Class III – Patients with marked limitation of activity; they are comfortable only at rest.

Class IV – Patients who should be at complete rest, confined to bed or chair; any physical activity brings on discomfort and symptoms occur at rest.

Throughout this protocol, "days" refers to calendar days, unless otherwise indicated.

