7.1 Pretreatment Evaluations

Pretreatment evaluations are used to determine the subject’s study eligibility and must be completed within 14 days prior to the first dose of study medication unless otherwise specified. Written informed consent must be obtained prior to any study-specific pretreatment evaluations. All subjects must undergo the following pretreatment evaluations:

- Medical history (any preexisting toxicity should be documented, recorded, and graded [NCI-CTCAE, Version 4.0 grade] as a part of the pretreatment history);
- Serum β -hCG pregnancy test in WOCBP (within 7 days prior to the first dose of study therapy);
- Baseline ECG;
- Baseline MUGA or echocardiogram for LVEF assessment (within 28 days prior to the first dose of study therapy);
- ECOG PS assessment;
- Complete physical examination (including height measurement);
- Vital signs (including temperature, pulse rate, respiration rate, and blood pressure);
- Weight measurement;
- Baseline toxicity/AE assessment;
- Concomitant medication assessment (including those medications taken 30 days prior to the first dose of study therapy);
- Hematology profile;
- Coagulation profile;
- Serum chemistry profile, including myoglobin;
- C-reactive protein assessment;
- Urinalysis;
- Blood samples for baseline PK analysis (on the day of and immediately prior to the first dose of study therapy), and immunogenicity and pharmacodynamic analyses (within 7 days prior to the first dose of study therapy);
- Blood samples for flow cytometry assessment and isoenzyme assessment of LDH, CK, and AP (within 7 days prior to the first dose of study therapy) for subjects in Cohort 2 and beyond;
- Blood sample for troponin (I or T) assessment (prior to the first infusion of Cycle 1 so that results are obtained before dosing);
- Blood sample for bone metabolism marker assessment (within 7 days prior to the first dose of study therapy);
- Imaging studies including a CT scan or MRI as described in Section 6.6 (performed and documented within 28 days prior to the first dose of study therapy);

- Bone scan, as clinically indicated (within 28 days prior to the first dose of study therapy; not required if PET is performed within 28 days prior to the first dose of study therapy that is negative for bone disease); and
- Tumor (core needle or excisional) biopsy (mandatory) (within 7 days prior to the first dose of study therapy) for subjects in Cohort 2 and beyond.

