- **Does not know:** The Investigator cannot determine.
- **Not related:** Without question, the AE is definitely not associated with the study treatment.

All "probably related," "possibly related," or "does not know" AEs will be defined as related to study drug/study procedure.

Subjects will be evaluated for AEs at each visit and will be instructed to call their study physician to report any AEs between visits.

NCI-CTCAE, Version 4.0 will serve as the reference document for grading the severity of all AEs and other symptoms. For AEs without matching terminology within the NCI-CTCAE, Version 4.0, the Investigator will be responsible for selecting the appropriate System Organ Class and assessing severity grade based on the intensity of the event.

In addition to collecting the AE verbatim and NCI-CTCAE severity grade, AE verbatim text will also be mapped by the Sponsor or designee to corresponding terminology within the Medical Dictionary for Regulatory Activities (MedDRA®).

If a subject's dosage is reduced or treatment is discontinued as a result of an AE, study site personnel must clearly report to the Sponsor or its designee via eCRF the circumstances and data leading to any such dosage reduction or discontinuation of treatment.

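### Inclusion criterion 3 requires recovery from only four kinds of prior therapy, so clinical toxicity from prior immunotherapy, antibodies or targeted agents can enter the trial and, if it worsens in Cycle 1, can be scored as a DLT

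*Protocol*

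**What the plan says.** **Recovery condition.** Protocol 3.2, criterion 3, asks for resolution to CTCAE Grade 1 or lower of "all clinically significant toxic effects of prior chemotherapy, surgery, radiotherapy, or hormonal therapy (with the exception of alopecia"). The synopsis names the same four modalities.

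**Washout conditions.** Protocol 3.3 deals with other prior treatments by time alone. Exclusion 3 reads: "The subject has received treatment with any monoclonal antibodies within 4 weeks prior to first dose of study therapy". Exclusion 6 covers other anticancer therapy, "including other chemotherapy, immunotherapy, chemoembolization, targeted therapy, or any investigational agent within 4 weeks prior to study entry". Neither asks whether toxicity from those treatments has settled. Exclusion 6 also lets some treatment run on: "Subjects with breast cancer may also continue with concurrent human epidermal growth factor receptor 2 (HER2)-directed therapy". Stable hormonal therapy for metastatic breast or prostate cancer may continue too.

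**Baseline handling.** Section 7.1 says that "any preexisting toxicity should be documented, recorded, and graded", but sets no grade that blocks entry.

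**Scoring in Cycle 1.** Section 4.1.4 limits DLTs to IMC-CS4-related events in Cycle 1 that do not improve to Grade 2 or lower within 7 days despite management. Nonhematologic events must be Grade 3 or 4. Under 8.1, the ratings *probably related*, *possibly related* and *does not know* are pooled: all such "AEs will be defined as related to study drug/study procedure". Under 4.1.1, two DLTs in a cohort of 3 to 6 stop escalation.

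**The concern.** Exclusions 3 and 6 treat antibodies, immunotherapy, targeted agents, chemoembolization and investigational agents as separate from the modalities in criterion 3, and they admit subjects who have had them. A washout is not recovery: colitis, pneumonitis, rash or neuropathy may outlast four weeks. Section 3.4 says the criteria must be followed explicitly, so the missing classes cannot simply be read into criterion 3.

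Two things are at stake. One is entry safety: the sponsor set a Grade 1 threshold, and it does not reach these classes. The other is DLT attribution. With 3 to 6 evaluable subjects per cohort, one misattributed event among the first three forces expansion and a second ends escalation. Section 1.4.4 says the DLT definition was revised for Part B together with an algorithm for early steroid treatment of immune-related events. A worsening of an earlier drug's immune toxicity may be hard to distinguish from a new event of that kind.

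**Working it through.** **Step 1: does another rule close the gap?**

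| Rule | What it catches | What it leaves |
|---|---|---|
| Criteria 5 to 9 (3.2) | Blood counts, liver, renal and coagulation tests, CK | Non-laboratory toxicity |
| Exclusions 11, 12 and 13 (3.3) | Cardiac disease and LVEF, liver disease, active bleeding | Gut, lung, skin, nerve and endocrine toxicity without these features |
| Exclusion 19 (3.3) | "The subject has any other serious uncontrolled medical disorders that, in the opinion of the Investigator", would compromise safety or participation | Toxicity above Grade 1 that the investigator does not judge serious and uncontrolled |
| Baseline grading (6.2, 7.1) | Recording only | No effect on eligibility |

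The residue is clinical, non-laboratory toxicity above Grade 1 from a class that criterion 3 does not name, and which the investigator does not judge serious and uncontrolled.

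**Step 2: can that residue become a DLT?** Every one of these must hold:

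1. The toxicity worsens on study. Section 12.5.2 counts an event that predates dosing as treatment-emergent only if it worsens.
2. It reaches Grade 3 or 4 in Cycle 1 (4.1.4).
3. It does not improve to Grade 2 or lower within 7 days despite management, including steroids if applicable (4.1.4).
4. The investigator chooses any rating except *not related*. Section 8.1 reserves that rating for events that are without question not associated with treatment, while *possibly related* requires only that a link is not impossible.

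The baseline-level exception in 4.1.4 applies to laboratory abnormalities, so clinical toxicities have no stated baseline adjustment. The route is narrow but open.

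**Step 3: scale, for illustration only.** The plan gives no figure to reproduce. Both inputs below are assumptions:

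- *p*: true drug DLT rate per subject.
- *q*: chance per subject, averaged over the whole cohort, that carried-over toxicity is scored as a DLT.

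The two are taken as independent, and the cohort as exactly 3 and then 3 more evaluable subjects. Then

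- effective rate: P = 1 − (1 − p)(1 − q)
- chance of stopping: S = 1 − [(1 − P)³ + 3P(1 − P)² × (1 − P)³]

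With p = 10%:

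| q | P | S |
|---|---|---|
| 0% | 0.100 | 9.4% |
| 1% | 1 − 0.9 × 0.99 = 0.109 | 10.9% |
| 2% | 1 − 0.9 × 0.98 = 0.118 | 12.5% |
| 5% | 1 − 0.9 × 0.95 = 0.145 | 17.6% |
| 10% | 1 − 0.9 × 0.90 = 0.190 | 27.0% |

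For q = 0: 0.9³ = 0.729; 3 × 0.1 × 0.81 × 0.729 = 0.177; S = 1 − 0.906 = 0.094.

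For q = 0%, 5% and 10%, S is 2.7%, 9.0% and 17.6% at p = 5%, and 29.1%, 37.8% and 46.4% at p = 20%.

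A value of q is a share times a chance. If one third of subjects carried such toxicity and 30% of those were scored as DLTs, q = 10%. If one sixth carried it and 10% were scored, q = 1.7% and S at p = 10% is 12.0%.

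**The case against.** The best reply is that carried-over toxicity faces several filters before it affects escalation. A stable Grade 2 toxicity is not a DLT. A flare that responds to steroids within 7 days is not one either. Preexisting toxicity is graded before dosing, and changes in it are recorded (8.1). The investigator must weigh disease, concomitant treatment and other pathology as causes (8.1). Table 10 calls for a workup of other etiologies, and a safety review meeting precedes every escalation (4.1.1). Many of the drug's own expected signals (9.1.3), such as transaminase and CK rises, are laboratory findings screened at entry by criteria 6 and 9. All of this stands, and it limits how often the problem can arise.

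It also rules out two stronger readings that a reader might infer. One is that any flare becomes a DLT because uncertain causality counts as related. Section 4.1.4 does not support that, since grade, timing and persistence must be met as well. The other is that an old toxicity cannot be told apart from a new one. The documents show only that this may be difficult: they provide baseline grading, a workup and a *not related* rating.

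The filters do not meet the entry point itself. They act after dosing, and none requires a named grade before the first dose for the omitted classes.

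A further objection is that a blanket rule could bar subjects whose earlier toxicity is permanent but controlled, such as endocrine deficiency on replacement. That is fair, and it is why exceptions need to be named.

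**Conclusion.** The gap in criterion 3 is real and is in the current text. As written, the plan admits clinical, non-laboratory toxicity above Grade 1 from prior antibodies, immunotherapy, targeted therapy, chemoembolization or investigational agents after a 4-week washout, subject to the investigator's judgment under exclusion 19.

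The effect on escalation is conditional and of unknown size. The documents do not give the share of subjects with such prior therapy, with unresolved toxicity, or with a flare. At a 10% drug DLT rate the effect is small at a carry-over rate of 1% or 2% (1.5 or 3.1 percentage points over 9.4%) and large at 10% (17.6 points). Nothing in the documents says which end applies, so the table should not be read as an estimate of bias in this trial.

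The case for change rests on the inconsistency between criterion 3 and exclusions 3 and 6, on entry safety, and on how little misattribution a cohort of 3 to 6 can absorb. It is an inexpensive improvement to make, and does not show that the escalation decisions would be wrong.

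**What to change.** In 3.2 criterion 3 and the matching synopsis criterion, apply the existing Grade 1 requirement to clinically significant toxicity of all prior anticancer therapy, including immunotherapy, monoclonal antibodies, targeted therapy, chemoembolization and investigational agents. The threshold itself does not change.

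The sponsor should also:

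- name any exceptions besides alopecia, considering stable toxicity controlled by replacement treatment;
- align the list of therapies with exclusions 3 and 6, whose 4-week periods run from different points (first dose and study entry);
- say how the rule applies to HER2-directed and hormonal therapy that may continue on study, where the word prior does not fit.

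The cost is a short wording change in an amendment. A few subjects would wait for toxicity to settle, and some whose toxicity does not settle and is not a named exception would be excluded.
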